6.3.3 Study Drug Discontinuation and Study Termination Criteria

Treatment with the study drug may be terminated/ discontinued for any of the following reasons:

- Serious adverse event (SAE);
- Failure to comply with the dosing, evaluations, or other requirements of the study;
- Unusual or excessive bleeding/signs or symptoms of abnormal bleeding from any source that cannot be controlled without discontinuation of the study drug administration (hematoma at the site of vascular sheath insertion may normally occur and should not serve as a reason to discontinue study drug unless bleeding cannot be controlled with normal measures).

Treatment with the study drug must be terminated/ discontinued for any of the following reasons:

- Request of the subject (subjects have the right to discontinue study drug administration at any time for any reason);

- There is a need for concomitant medication(s), which makes the subject ineligible to receive the study drug;
- Pregnancy; or
- Anaphylaxis.

In addition, if a subject who does not meet enrollment criteria is inadvertently randomized in the study, the sponsor must be notified. Although the subject should be discontinued from receiving study drug treatment, an exception may be granted by the sponsor if there is a compelling reason to continue with the administration of the study drug, but the investigator must obtain documented approval from the sponsor.

It is the right and duty of the investigator or sub-investigator to interrupt/stop study drug treatment of any subject if he/she feels that it is necessary to protect the subject, or that there are unmanageable factors, that may interfere significantly with the study procedures and/or the interpretation of results. If the study drug is discontinued prior to the completion of the infusion, the reason for the discontinuation will be obtained. This information will be documented in source records and in the appropriate section of the electronic case report form (eCRF) and the Sponsor should be notified promptly. Every effort should be made to ensure all activities outlined in the **Section 1.2**, Study Flow Chart and **Section 6.5**, Study Schedule are performed as usual.

Normal study termination/discontinuation is defined as the completion of all visits and procedures listed under **Section 1.2**. Early study termination/discontinuation occurs if the subject fails to complete the entire study, through to the 90-day telephone follow-up. Early termination from the study may occur for the following reasons:

- Subjects are free to withdraw from the study at any time for any reason- formal withdrawal of the subject's consent to participate further in any of the remaining study procedures must be documented by the investigator/qualified designee;
- In the opinion of the investigator, the subject cannot safely perform the procedures required by the protocol (e.g., adverse event, concomitant treatment);
- Subject does not comply with the protocol instructions given by the investigator/qualified designee;
- The subject becomes pregnant (pregnancy will be followed as per **Section 6.7.2.2.7**);
- The sponsor, Tufts Medical Center may terminate the study for any reason;
- The study may be terminated at any time by the national or local regulatory authorities overseeing and/or funding the trial (e.g., FDA, NHLBI/NIH, or IRB).

A subject has the right to discontinue participation in the study at any time for any reason without prejudice to his/her future medical care by the investigator or at the institution. Withdrawal of partial consent means that the subject does not wish to receive the study drug any longer but is still willing to collaborate in providing further data by continuing on study (e.g., participate in subsequent study visits/contacts or procedures, allow release of follow-up

information). Withdrawal of full consent means that the subject does not wish to receive further study drug and does not wish to or is unable to continue further study participation; subject data up to withdrawal of consent will be included in the subjects' study data. Withdrawal of partial or full consent by the subject must be documented in writing by the investigator/qualified designee. The investigator will discuss with the subject appropriate procedures for withdrawal from the study drug and/or study. Should a subject request or decide to withdraw from the study, all efforts will be made to complete and report the observations as thoroughly as possible up to the date of withdrawal. All information should be reported on the applicable eCRFs and the Sponsor should be notified promptly.

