6.2 Participation in and Completion of the Study

The subject is considered to be enrolled in the study when the subject is successfully randomized and is assigned a study drug treatment regimen and a unique subject randomization number. A subject who receives a randomization assignment without ever receiving any amount of study drug treatment (“randomized but not treated”) is still part of the intent-to-treat (ITT) data set for efficacy endpoints and must be followed thereafter per protocol (a telephone contact may be used in lieu of the 14-day follow-up visit for those not having taken any amount of study drug). A subject who signs the informed consent to participate in the study but does not undergo a successful randomization (i.e., screen failure, withdrew consent) will not be followed beyond the point it is determined that the subject will not be randomized- no further data will be collected and the subject will not be included in safety or efficacy analyses. Information on subjects who are screened and consented for the study but fail to undergo randomization will be submitted to the sponsor as per **Section 8.2** for regulatory purposes and to establish that the study population was selected without bias.

The subject is considered to have completed the study drug treatment following cessation of the study drug infusion. Given the single-dose design of the study, once the subject has received the study drug infusion (or once a subject permanently discontinues the study drug infusion), the study drug will no longer be available to the subject.

The subject is considered to have completed the entire study when he/she has undergone the final protocol-specified contact (i.e., study telephone call at 90-days following the study drug administration). Subject participation may be terminated prior to completion for reasons described in **Section 6.3.3**. For those subjects who do not complete the entire study protocol, subject participation will be considered terminated upon the completion of the last visit or phone contact.

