6.3.4 Replacement of Subjects

Subjects who are randomized, but who discontinue from the study prior to receiving any amount of study drug may be replaced.

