6.6 Study Procedures

The Study Flow Chart in **Section 1.2** summarizes the study procedures to be performed at each protocol time point. Individual study procedures are described below. For details of the procedures for assessment and reporting of adverse events, see **Section 6.7.2.2** (Assessment and Reporting of Adverse Events).

In order to minimize variability of evaluations, it is recommended that the same individuals perform the same types of evaluations for all subjects at each clinical site.

If a subject's participation in the study is discontinued for any reason, every attempt should be made to obtain final information for each test and evaluation as shown in the Study Flow Chart in **Section 1.2** pending the subject's consent to undergo the study-directed procedures and permission to disclose the corresponding information/data.

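### Section 6.3.3 lets a subject's study participation end early without withdrawal of consent, and nothing clearly requires the day-30 and day-90 outcome contacts afterwards, so later bleeding or MACE can be missed and counted as no event

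*Combined protocol and SAP*

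**What the plan says.** Section 6.3.3 treats stopping study drug and leaving the study separately. For leaving the study it says: "Early study termination/discontinuation occurs if the subject fails to complete the entire study, through to the 90-day telephone follow-up". Withdrawal by the subject is one listed reason. Three others need no such wish:

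- investigator judgement: "In the opinion of the investigator, the subject cannot safely perform the procedures required by the protocol (e.g., adverse event, concomitant treatment";
- non-compliance: "Subject does not comply with the protocol instructions given by the investigator/qualified designee";
- pregnancy, where the cross-reference covers follow-up of the pregnancy itself.

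For consent, 6.3.3 distinguishes partial withdrawal (no more drug, data still provided) from full withdrawal. It makes no such distinction for these three reasons. For anyone who does not complete the protocol, Section 6.2 states that "subject participation will be considered terminated upon the completion of the last visit or phone contact".

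Other passages pull towards continued follow-up:

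- When the infusion is stopped early, 6.3.3 says "Every effort should be made to ensure all activities outlined in the" flow chart and study schedule are carried out as usual.
- When participation stops for any reason, Section 6.6 says "every attempt should be made to obtain final information for each test and evaluation as shown in the Study Flow Chart", subject to the subject's consent.
- Sections 6.6.1 and 6.7.2.2 require reporting of all adverse events to day 30, and of SAEs and efficacy endpoint events to day 90. Sections 6.7.2.2.5 and 6.7.2.2.6 require SAE and death reports to day 90. No exemption is stated for subjects who have left.
- Section 6.2 says that a subject randomised but never dosed "is still part of the intent-to-treat (ITT) data set for efficacy endpoints and must be followed thereafter per protocol".

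Section 7.2 makes the primary and secondary outcomes binary and classes everyone without an event in the window as negative. It leaves data-handling conventions to a later SAP. The statistical section gives no rule for incomplete follow-up.

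**The concern.** Treatment is a single 2-hour infusion, and follow-up after discharge is one visit and two telephone calls. A safety worry may justify omitting a procedure. It does not obviously justify omitting a call or a records check, yet 6.3.3 allows the whole of participation to end.

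The exit reasons may be related to treatment or prognosis. Section 6.6.1 names allergic reaction as a known PZ-128 side effect, and an adverse event or new treatment after catheterisation can mark a subject at higher risk of a later event. Under the binary rule, a subject who leaves on day 3 and has an unreported TIMI minor bleed on day 12 enters the primary analysis as event-free. In a non-inferiority comparison of harm, under-recording more easily hides an excess than creates one. The 90-day MACE result faces the same risk. Its Kaplan-Meier and Cox analyses could censor such subjects instead, but censoring at an exit of this kind need not be uninformative.

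**Working it through.** **Step 1. What the passages require together.**

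| Situation | Rule | Day-30 and day-90 contact clearly required? |
|---|---|---|
| Infusion stopped early, subject stays in study | 6.3.3, every effort to perform all scheduled activities | Yes, as best effort |
| Randomised, never dosed, stays in study | 6.2, must be followed | Yes |
| Study participation ended by investigator judgement, non-compliance or pregnancy | 6.2, over at last contact; 6.6, every attempt at final information | Not clear |

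In the third row, 6.6 refers to the flow chart, which contains both calls, but it speaks of final information and does not say that the calls go ahead. The reporting windows stay open, but a site must learn of an event to report it, and 6.5.10 and 6.5.11 make the calls the scheduled occasion for asking. A TIMI minor bleed is an overt bleed with a haemoglobin fall of 3 to <5 g/dL (6.7.1.1). It counts towards the primary endpoint without necessarily meeting the SAE definition.

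**Step 2. The plan's own margin.** Section 7.7 lists 2.6 points for placebo risk 2% and true difference 0, with 400:200 subjects, 80% power and a one-sided 95% bound. The unpooled normal formula gives

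(1.645 + 0.842) × √(0.02×0.98/400 + 0.02×0.98/200) = 2.487 × 0.01212 = 3.0 points.

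The listed 2.6 is not reproduced at one-sided 5%. That is a separate matter. The listed margins serve below only as reference values, because 7.5.4 fixes no margin.

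**Step 3. Direction and size of the shift.** Let e be the fraction of an arm that leaves this way, and r the risk of a first qualifying event after leaving that goes unrecorded. Then

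shift in risk difference = −(e₁r₁ − e₀r₀), where 1 = PZ-128 and 0 = placebo.

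The shift favours non-inferiority when e₁r₁ > e₀r₀. It is zero when the products are equal and reverses if placebo loses more. The documents give neither e nor r, so these are assumptions:

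- e₁ = 2% (8 of 400), r₁ = 2%, e₀ = 0: 0.16 events, 0.04 points.
- e₁ = 5% (20 of 400), r₁ = 8% (the plan's highest implied rate, 6% + 2%), e₀ = 0: 1.6 events, 0.4 points.
- e₁ = 5%, r₁ = 20% (leavers at raised risk), e₀ = 0: 4 events, 1.0 points.
- e₁ = e₀ = 5%, r₁ = 8%, r₀ = 6%: 0.05 × 2 = 0.1 points.

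**Step 4. Effect on a false conclusion.** Set the true difference equal to the listed margin, so that non-inferiority should be concluded in at most about 5% of trials. Let a fraction f of PZ-128 events go unrecorded and no placebo events. Exact binomial probability that the one-sided 95% Wald bound lies below the margin:

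| Placebo risk / margin | PZ-128 events expected | f = 0 | f = 10% (events missed) | f = 20% (events missed) |
|---|---|---|---|---|
| 2% / 2.6 | 400 × 4.6% = 18.4 | 4% | 8% (1.8) | 15% (3.7) |
| 4% / 3.7 | 400 × 7.7% = 30.8 | 4% | 10% (3.1) | 20% (6.2) |
| 6% / 4.4 | 400 × 10.4% = 41.6 | 4% | 11% (4.2) | 23% (8.3) |

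Step 3 gave at most 4 missed events. That is 22% of 18.4, 13% of 30.8 and 10% of 41.6, so the last column in the lower two rows lies beyond the assumed range.

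**The case against.** The best defence is that the protocol already intends follow-up. The investigator clause is permissive, and its test is whether procedures can be performed safely; the adverse event and the concomitant treatment are only examples. A telephone call hardly fails that test. Section 6.6 asks for every attempt after discontinuation for any reason, and the reporting windows have no exemption for leavers. This stands in part: it reduces the likely loss and means that the plan does not prescribe loss. It does not make the calls mandatory, and non-compliance and pregnancy carry no safety test.

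A reader might infer more than the text supports:

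- *That outcomes are lost.* They can be lost. A qualifying bleed that itself leads to exit is already counted, and the primary endpoint needs only one.
- *That 6.6 asks for information only at the point of leaving.* It sets no such limit.
- *That dosed subjects may be dropped while never-dosed subjects must be kept.* The 6.3.3 reasons cover all subjects, and 6.3.4 says: "Subjects who are randomized, but who discontinue from the study prior to receiving any amount of study drug may be replaced". Never-dosed subjects are also outside the safety set (7.3), so this contrast cannot bias the primary result.
- *That starting an anticoagulant ends follow-up.* Section 6.4.3 allows it after sheath removal where specifically indicated, and 6.4.8.1.1 asks that the sponsor be contacted if an oral one is essential in the restricted period.
- *That allergic reactions will concentrate loss on PZ-128.* Reactions during infusion are handled by interrupting or stopping the drug (6.4.7.7, 6.7.2.3), after which 6.3.3 asks for all activities as usual.

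**Conclusion.** The concern holds as a gap in outcome follow-up. Sections 6.3.3 and 6.2 allow participation to end before day 90 without withdrawal of consent. Section 6.6 and the reporting windows soften this without clearly requiring the two outcome contacts, and 7.2 turns an unrecorded event into a non-event. The bias favours non-inferiority when more PZ-128 than placebo risk goes unrecorded, which includes equal proportional loss when PZ-128 truly causes more bleeding. The documents do not show that exits will be commoner on PZ-128.

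The size cannot be derived from the documents. The range of 0.04 to 1.0 points rests on assumed exit fractions and later risks, with all loss placed on PZ-128. Equal exits in both arms give far less, 0.1 points in the example, and possibly none. The false-conclusion figures also depend on an assumed f and use listed margins that the plan does not adopt as a decision rule. The point is worth correcting because the potential effect is material and the correction is small.

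**What to change.** In 6.3.3, keep investigator judgement, non-compliance and pregnancy as grounds for stopping particular study procedures or visits, but not outcome follow-up. The investigator's safety clause stays. Reconcile 6.3.3 and 6.2 with 6.6 so that all three say the same thing about subjects who stop procedures.

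Add that every randomised subject is contacted by telephone, or has records checked, for bleeding, MACE and death at days 30 and 90 unless consent to that contact is withdrawn. Allow a telephone contact in place of the 14-day visit, as 6.2 already does for undosed subjects. In the SAP, state how subjects with incomplete outcome follow-up are handled under the 7.2 binary rule, and add a sensitivity analysis that does not class them all as negative.

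Both calls are already scheduled. The cost is a short protocol edit and a few extra calls or records checks. The planned sample size does not change.

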6.3.4 Replacement of Subjects

Subjects who are randomized, but who discontinue from the study prior to receiving any amount of study drug may be replaced.

6.4 Study Treatments

The investigator or qualified designee is responsible for delivering the investigational therapy and any required co-administered therapy and the standard of care treatment(s) outlined according to the protocol and verifying compliance in source documentation and on the eCRF, and ensuring that any other therapy not specified in the protocol is delivered according to the local standard of care.

6.4.1 Blinded Investigational Study Drugs

Approximately 600 subjects will be randomized in a 2:1 (PZ-128: PZ-128 placebo) ratio to receive 1 of the following 4 treatment assignments:

- Single, 2-h IV infusion of PZ-128 0.3 mg/kg
- Single, 2-h IV infusion of PZ-128 0.5 mg/kg
- Single, 2-h IV infusion of Placebo 0.3 mg/kg
- Single, 2-h IV infusion of Placebo 0.5 mg/kg

The PZ-128 active drug and matching placebo are provided as vials of solid lyophilized powder cake for reconstitution and will be indistinguishable. The individualized dose will be based upon the baseline (i.e., Screening) weight of the subject and the dose level assignment by the centralized randomization system used as part of the method of treatment assignment (**Section 6.4.4**). The type and number of vials of study drug will be selected by an unblinded investigational pharmacist (**Section 6.4.6**) at the clinical site who is able to obtain the subject's unmasked randomized treatment assignment via a restricted access login within the randomization system. Each vial of study drug will be reconstituted with 10 mL of Sterile Water for Injection, USP (SWFI) and the calculated amount of reconstituted volume of study drug will be mixed and diluted with 250 mL (plus the manufacturer's overfill volume) of Dextrose 5% in Water, USP (D5W) to yield a final IV bag (blinded) for administration.

PZ-128 or matching placebo, as determined by the randomization scheme, will be administered by a qualified member of the study staff or institution's clinical staff over a 2-hour continuous IV infusion and the infusion must begin 0-60 min prior to the start of the cardiac catheterization (i.e., diagnostic coronary angiography). The infusion will run through completion regardless of whether the subject progresses to PCI, CABG or medical management.

[REDACTED] The peripheral IV line for the drug infusion should not be smaller than 20-gauge. Flushing of the IV access site (not the line) will be done using 0.9% Sodium Chloride for Injection (Normal Saline).

[REDACTED]

[REDACTED]

[REDACTED]

[REDACTED]

[REDACTED]

6.4.3 Other Required and Potential Rescue Treatment(s) (Standard of Care)

Investigators will use current applicable standard of care guidelines, the individual's clinical circumstances, and the local practices for the procedures surrounding the cardiac catheterization ± PCI and follow-up care post cardiac catheterization ± PCI [47].

Standard of care treatments/parameters in the context of this study will include oral anti-platelet therapy- aspirin and P2Y₁₂ inhibitor (i.e., clopidogrel, prasugrel, or ticagrelor), an anti-coagulant (i.e., unfractionated heparin or low-molecular-weight heparin) and potential rescue therapy (thrombotic bailout) with a GP IIb/IIIa inhibitor (e.g., eptifibatide). These treatments administered/taken within 30 days prior to randomization and at any time during the study must be documented in the subject's source documents/medical records and recorded in the "Previous and Concomitant Medication" module of the eCRF.

- **Aspirin:** Subjects not on aspirin therapy should be given nonenteric aspirin 325 mg before the study drug administration (subjects already taking daily aspirin therapy should take 81-325 mg before the study drug administration). After the cardiac

catheterization/PCI aspirin 81-325 mg daily may be continued indefinitely. ASA for pain relief should where possible be discouraged and acetaminophen given.

- **P2Y₁₂ Inhibitor(s):** A loading dose of an FDA-approved oral P2Y₁₂ inhibitor should be given to subjects before PCI with stenting (dosing may be adjusted depending upon prior chronic use of oral P2Y₁₂). Investigator discretion will be used and options include the following:
 - Clopidogrel (Plavix[®]) 600 mg
 - Prasugrel (Effient[®]) 60 mg
 - Ticagrelor (Brilinta[®]) 180 mg

The choice and duration of oral P2Y₁₂ inhibitor therapy after stent implantation will be as per investigator discretion. Options include the following FDA-approved drugs:

- Clopidogrel (Plavix[®]) 75 mg daily
 - Prasugrel (Effient[®]) 5-10 mg daily
 - Ticagrelor (Brilinta[®]) 90 mg twice daily
- **Anticoagulant:** An anticoagulant should be administered to subjects undergoing PCI. Following administration of the initial bolus of anticoagulant, activated clotting time (ACT) will be measured locally at “peak dose” and just prior to sheath removal, as well as according to the standard of care.
 - Administration of IV Unfractionated Heparin (UFH) is preferred in this study and should be dosed per standard of care and routine hospital practice (i.e., weight-based and adjusted to attain target ACT).
 - Low-molecular-weight heparin (LMWH) is an acceptable alternative to UFH within the context of this trial (weight adjusted in accordance with approved dosage and administration).
 - It is strongly recommended to use only one anti-coagulant drug consistently and not switch between agents before or during the PCI procedures.
 - A parenteral direct thrombin inhibitor (e.g, bivalirudin) is not to be administered.
 - Anticoagulant should not be restarted after access sheath removal unless specifically indicated for another condition such as anticoagulation for a deep venous thrombosis, atrial fibrillation, or a mechanical prosthetic heart valve (**Section 6.3.2**).
 - **Rescue Therapy (thrombotic bailout):** The planned administration of GP IIb/IIIa inhibitors (GPI) for a subject excludes that subject from participation in this study and therefore should not be an anticipated part of the regimen. During PCI, bail-out with an FDA-approved GPI such as eptifibatid (Integrilin[®]) may be used, at the investigator’s

discretion, in subjects with new ischemia on telemetry or ECG, worsening of angiographic coronary flow during procedure or thrombotic complication(s) related to stenting during or after PCI.

- **Coronary Stents:** During PCI, the number and type of coronary stenting will be determined by the investigator and will include only FDA-approved devices (bare metal and drug-eluting) which are indicated for PCI. The stent implant procedure will be performed in accordance with the device Instructions for Use (IFU).
- **Vascular Access and Closure Devices:** The use of radial, femoral or brachial artery access will be allowed. Timing of the arterial sheath removal will be performed as per standard of care and local routine practice (e.g., target ACT). FDA-approved vascular closure devices (e.g., Angioseal™, Vasoseal™, Perclose™) may be used as an alternative to manual compression to attain vascular hemostasis. Pressure on the access site (either manual or by a mechanical device) should be applied for a minimum of 30 minutes.

